11. SUBJECT CHARACTERISTICS AND DEMOGRAPHICS

11.1 Enrollment and Disposition of Subjects

A summary table will include all subjects and present the total number of subjects consented, treated (including on treatment, off treatment, in follow-up, and off study), and in each analysis population. In addition, the number and percentage of the study treatment termination reasons and the study discontinuation reasons will be presented. The percentages will be based on the total number of subjects treated.

Subjects who discontinued the study 30 or fewer days from the last dose of study drug are considered to have discontinued the study during the treatment period. Subjects who discontinue the study more than 30 days after the last dose of study drug are considered to have discontinued the study while in follow-up.

11.2 Protocol Deviations

Protocol deviations will be listed for all subjects in the SP for whom deviations were reported. The listing will include the deviation classification (major or minor) as well as the deviation category.

11.3 Demographics and Baseline Characteristics

Descriptive statistics will be generated for all demographic and baseline characteristics by dose level and cancer type in order to descriptively assess the comparability of the cohorts. The variables to be summarized are:

Demographics -

- Age at enrollment,
- Date of Birth (listing only),
- Sex,
- Child-bearing potential,
- Race and
- Ethnicity

Baseline subject characteristics –

- Height (cm),
- Weight (kg),
- ECOG Performance Status, and
- Cigarette smoking history:
 - Current versus former smokers,
 - Years since last use,
 - Number of packs per day, and
 - Years of tobacco use.
- Subject cancer type and characterization:
 - Time since initial histopathological diagnosis (years),
 - Time since the most recent disease recurrent/progression (years),
 - Cancer type,
 - Stage at Study Entry,
 - CD166 Status at Baseline
 - Disease characterization (Locally Advanced unresectable, Metastatic),

- Whether or not the disease is measurable,
- Subject prior cancer treatment:
 - Number of prior cancer treatment regimens per subject
 - Time since last prior cancer treatment end date (weeks)
 - Prior use of platinum-containing compounds (Yes/No)
 - Prior use of anti-PD-1/anti-PD-L1 treatment (Yes/No)
 - Prior use of any microtubule inhibitor (Yes/No)
 - Prior use of any platinum-containing compounds or microtubule inhibitor (Yes/No)
 - Prior radiotherapy (Yes/No)
 - Time since last prior cancer procedure (weeks)

Categories for platinum-containing compounds, anti-PD-1/anti-PD-L1 treatment, microtubule inhibitors will be based on a search list provided by CytomX prior to the database lock.

Other prior cancer treatment information including the regimen or procedure, treatment duration, best overall response, reason for therapy ended, and time since disease progression will be captured in a listing.

12. Safety and Tolerability Analysis

The primary objectives of the study is to evaluate the safety and tolerability of multiple doses of CX-2009, administered as monotherapy to subjects with advanced solid tumors and to determine the MTD and DLTs of CX-2009.

Safety will be assessed on the basis of AEs, clinical laboratory data, vital signs, ECG parameters, and physical examinations. Dosing and exposure to CX-2009 will be presented.

All safety data will be listed by subject within part and dose cohort in chronological order. Summary tabulations of safety data will be performed as noted in the following sections.

12.1 Adverse Events and Serious Adverse Events

Adverse events will be collected from start of treatment through the follow-up period. Serious adverse events occurring during the screening period will be collected on the Adverse Events form. All other AEs occurring during the screening period will be collected on the Medical History form.

Adverse events will be coded in accordance with the Medical Dictionary for Regulatory Activities (MedDRA) Version 23.0. Adverse events will also be graded by the National Cancer Institute - Common Terminology Criteria for Adverse Events (NCI-CTCAE) v4.03.

Only treatment-emergent adverse events (TEAE) occurring and reported while on-treatment and up to and including 30 days after the last dose of study drug will be included in the adverse event summaries. A treatment-emergent AE is an event that emerges during treatment (including on or after the day of Zr-CX-2009 treatment in subjects enrolled in the CTMX-M-2009-001 imaging substudy) having been absent pre-treatment, or worsens relative to the pre-treatment state. AEs occurring between informed consent and first dose as well as AEs occurring 31 or more days after last dose will be listed.

AE presentation will include incidence, grade (by NCI-CTCAE criteria), and relationship to study drug.

An Investigator's causality assessment is the determination of whether there exists a reasonable possibility that the study drug caused or contributed to an adverse event. The relationship to study drug will be categorized as "Related" or "Not Related." Related AEs/SAEs are those judged by the Investigator to be definitely, probably, or possibly related or Unknown relationship to a study drug.

TEAEs, including serious TEAEs, will be listed by subject within part and dose cohort in chronological order of AE start date/time.

The verbatim term and MedDRA system organ class (SOC) and preferred term (PT) will be included in the listings along with start and end dates, time on study, severity, seriousness, relationship of the event to study drugs, action taken with the study drugs, other action taken, outcome, infusion reaction (IR) (Y/N), DLT (Y/N), and AE of special interest (AESI) (Y/N).

The following listings will be provided:

- TEAEs
- TEAEs with CTCAE Grade 3 or Higher
- TEAEs related to CX-2009
- TEAEs related to CX-2009 with CTCAE Grade 3 or Higher
- Infusion reactions
- TEAEs leading to discontinuation of study drug
- TEAEs leading to death
- All SAEs
- SAEs related to CX-2009
- SAEs related to CX-2009 with CTCAE Grade 3 or higher
- TEAE of Special Interest
- DLT AEs
- Deaths

If there are no subjects who meet the criteria for any of these listings, the listing will be generated and will contain a statement, "No <criteria> were reported." for example, if there are no deaths on study, the statement would be "No deaths were reported."

Overall AE summary tables will each be prepared by dose level, by cancer type, and by Breast Cancer cohort (TNBC, HR+/HER2-, HER2+), and will include the number and percentage of subjects with reports of:

- TEAEs
- TEAEs related to CX-2009
- TEAEs with CTCAE Grade 3 or higher
- TEAEs with CTCAE Grade 3 or higher related to CX-2009
- TEAEs classified as infusion reactions
- TEAEs classified as infusion reactions with CTCAE Grade 3 or higher
- TEAEs leading to study drug discontinuation
- TEAEs leading to study drug discontinuation and related to CX-2009

- Dose-Limiting Toxicities (DLTs)
- Treatment-emergent SAEs (TESAEs)
- TESAE related to CX-2009
- TEAEs leading to death
- TEAEs leading to death and related to CX-2009
- TEAEs of Special Interest
- TEAEs of Special Interest with CTCAE Grade 3 or higher
- TEAEs of Ocular Toxicity related to CX-2009
- TEAEs of Ocular Toxicity related to CX-2009 with CTCAE Grade 3 or higher
- TEAEs of Neuropathy related to CX-2009
- TEAEs of Neuropathy related to CX-2009 with CTCAE Grade 3 or higher
- TEAEs of Hepatic Disorders related to CX-2009
- TEAEs of Hepatic Disorders related to CX-2009 with CTCAE Grade 3 or higher

This overall AE summary table will also be produced for the DSMB meetings. TEAEs categorized as Ocular Toxicity, Neuropathy, or Hepatic Disorders will be defined based on a search list provided by CytomX prior to database lock.

Only TEAEs (excluding unrelated, fatal AEs with PT="Malignant neoplasm progression") will be included in the AE summaries and be tabulated by MedDRA SOC and PT within part and dose cohort. Tables presenting summaries of frequencies and percentages of subjects reporting at least one TEAE within each MedDRA SOC and PT by dose level and by cancer type will be provided for TEAEs and TESAEs as follows:

- All TEAEs
- Grade 3 or higher TEAEs
- TEAEs related to CX-2009
- TEAEs related to CX-2009 by maximum severity grade
- Grade 3 or higher TEAEs related to CX-2009
- Grade 3 or higher TEAEs related to CX-2009 by maximum severity grade
- TEAEs leading to study drug discontinuation
- TEAEs leading to death
- TEAEs leading to death related to CX-2009
- TEAEs of Special Interest by maximum severity grade
- TEAEs of Ocular Toxicity related to CX-2009 by maximum severity grade
- TEAEs of Neuropathy related to CX-2009 by maximum severity grade
- TEAEs of Hepatic Disorders related to CX-2009 by maximum severity grade
- TESAEs
- Grade 3 or higher TESAEs
- Grade 3 or higher TESAEs related to CX-2009

Each subject will be counted only once within each level of the summary (PT or SOC). If a subject experiences more than one TEAE within a PT or SOC, only the TEAE with the strongest relationship or the maximum severity, as appropriate, will be included in the summaries of relationship and severity.

The above list of summary tables will also be produced by MedDRA PT (based on descending frequency of the total column) by dose level or by cancer type.

The TEAE summary tables by SOC and PT will be provided upon request to the DSMB.

TEAE profile summaries will also be created for infusion reactions. This table will summarize the frequency of events, time from event onset to the start time of the first infusion (hours), time from the event onset to the start time of the most recent infusion (hours), duration of the event (hours), duration category (<1 hour, 1 to 6 hours, >6 hours), severity grade, outcome, action taken, and other action taken with medication.

Profile summaries will also be created for TEAEs of Ocular Toxicity, TEAEs of Neuropathy, and TEAEs of Hepatic Disorders. These tables will summarize the time from event onset to the start time of the first infusion (days), duration of the event (days), duration category (<=7 days, 7 to 14 days, >14 days), severity grade, outcome, action taken, and other action taken with medication.

A tabular summary of deaths by study period (Screening, Treatment, Follow-Up) will be provided by dose level and by cancer type.

No inferential statistical tests will be performed for safety analyses.

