8 SAFETY ASSESSMENTS

8.1 Adverse Events

An AE is defined as any untoward medical occurrence in a clinical investigation subject administered a pharmaceutical product, which does not necessarily have a causal relationship with this treatment. An AE can therefore be any unfavorable and/or unintended sign (including an abnormal laboratory finding), symptom, or disease temporally associated with the use of an investigational medicinal product, whether or not related to the investigational medicinal product. All AEs, including observed or volunteered problems, complaints, or symptoms, are to be recorded on the appropriate eCRF.

Progressive disease in and of itself is not considered an AE or SAE. Progressive disease is an efficacy finding and should not be reported unless the progressive disease results in death during the reporting period (from date of signed informed consent to 30 days post last study treatment administration). On-study deaths, reported as SAEs due to progressive disease and considered unrelated to study drug will be excluded from treatment-emergent AE analysis.

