8.1.3 Serious Adverse Event or Serious Suspected Adverse Reaction

An AE or suspected adverse reaction is considered “serious” if, in the view of either the Investigator or Sponsor, it results in any of the following outcomes:

- Death
- A life-threatening AE (see definition above)
- Inpatient hospitalization or prolongation of existing hospitalization
- A persistent or significant incapacity or substantial disruption of the ability to conduct normal life functions

- A congenital anomaly/birth defect
- Important medical events: Based on medical judgment, may jeopardize the subject or may require medical or surgical intervention to prevent one of the outcomes listed above (eg, anaphylaxis, allergic bronchospasm requiring intensive treatment in an emergency room or at home, blood dyscrasias or convulsions that do not result in inpatient hospitalization).

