8.2.2 Severity

The severity of an event describes the degree of impact upon the subject and/or the need for, and extent of, medical care necessary to treat the event.

AE grading will be defined by the NCI CTCAE v4.03. In the event that the NCI CTCAE v4.03 does not apply, the severity descriptions in [Table 11](#) will be used to describe the maximum intensity of the AE.

Table 11. Adverse Event Severity

Grade	Description
Grade 1	Mild; asymptomatic or mild symptoms; clinical or diagnostic observations only; intervention not indicated
Grade 2	Moderate; minimal, local or noninvasive intervention indicated; limiting age-appropriate instrumental activities of daily living.
Grade 3	Severe or medically significant but not immediately life-threatening; hospitalization or prolongation of hospitalization indicated; disabling; limiting self-care activities of daily living
Grade 4	Life-threatening consequences; urgent intervention required
Grade 5	Death related to an adverse event

Source: https://www.eortc.be/services/doc/ctc/CTCAE_4.03_2010-06-14_QuickReference_5x7.pdf. Accessed 19 November 2019.

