9.2 Other Statistical Analyses

Statistical assessments/methods for safety, efficacy, PK/PD, and immunogenicity are found in Section 11 of the Core. In instances where the statistical analysis plan (SAP) might contradict the analyses specified in the Core, the SAP supersedes the Core.

Available data from Part A2 will be pooled with data from Part A by dose. In addition, efficacy data from Part A2 may be analyzed separately. The relationship between dose and safety/efficacy may be explored. Analyses by dose may be conducted for, but not limited to, the following endpoints: frequency of AEs of special interest, ORR, and percent reduction in tumor burden by dose. A generalized linear model may be used to adjust for covariates or to model the relationship. Because of the limited number of subjects, the above analyses will be conducted if data warrant.

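### SAP 12.1 excludes unrelated progression deaths from the AE tables only under one preferred term, whereas Module 8.1 sets no coding condition

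*SAP*

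**What the plan says.** Module 8.1 does not treat progression itself as an adverse event. It says that progressive disease "should not be reported unless the progressive disease results in death during the reporting period", so fatal progression can enter the AE data. The next sentence sets the analysis rule: "On-study deaths, reported as SAEs due to progressive disease and considered unrelated to study drug will be excluded from treatment-emergent AE analysis". That rule tests cause as reported and relatedness, and does not mention coding.

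SAP 12.1 states its own rule where it introduces the tables by system organ class and preferred term: "Only TEAEs (excluding unrelated, fatal AEs with PT='Malignant neoplasm progression') will be included in the AE summaries". Three conditions must all hold: unrelated, fatal, and that one preferred term. On the source of the term, the SAP says "Adverse events will be coded in accordance with the Medical Dictionary for Regulatory Activities (MedDRA) Version 23.0". Verbatim term and code are separate data items, since "The verbatim term and MedDRA system organ class (SOC) and preferred term (PT) will be included in the listings".

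On precedence, Module 9.2 says: "In instances where the statistical analysis plan (SAP) might contradict the analyses specified in the Core, the SAP supersedes the Core". It does not address a conflict between the SAP and the Module.

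**The concern.** The two rules define different sets of excluded events. The SAP set can be smaller than the Module set, because it carries an additional coding condition. Neither document requires one term for progression deaths, names equivalent preferred terms, or plans a review to decide which deaths are excluded. For ocular, neuropathy and hepatic events, by contrast, SAP 12.1 uses sponsor search lists supplied before database lock.

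At stake are the all-causality rows for TEAEs leading to death, serious TEAEs and Grade 3 or higher TEAEs, which are tabulated by dose level and by cancer type. Several dose groups have fewer than ten subjects, so one event retained or removed visibly changes a rate. The reader would take the rate as following the protocol definition when it also reflects a code.

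**Working it through.** **Which events fall between the rules.** Take an on-study death reported as an SAE due to progressive disease and judged unrelated.

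- Coded to *Malignant neoplasm progression*: excluded by both documents.
- Coded to any other preferred term: excluded by Module 8.1, counted by SAP 12.1.
- Judged related: counted by both. A missing relationship is set to related under SAP 10.1.2, and an unknown one counts as related under SAP 12.1.

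Only the second case differs, and it is unrelated by definition. Tables of related TEAEs therefore cannot change.

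**Which rows change.** A fatal event is Grade 5, described in Module 8.2.2 as "Death related to an adverse event". Under Module 8.1.3 an event is serious if "it results in any of the following outcomes", and death heads that list. A retained death is thus counted as fatal, serious and Grade 3 or higher.

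**Which tables.** The exclusion sentence clearly governs the tables by system organ class and preferred term. The overall AE summary table is specified before that sentence and is also produced for the DSMB. The text does not make clear whether the exclusion applies to it.

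**Size.** The plan gives no figure to reproduce and the documents give no count of such deaths. The step is therefore shown for an assumed k = 1 to 3:

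increase in fatal-TEAE rate = 100 × k / n percentage points, provided the subject has no other fatal TEAE on record.

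The total of 99 is from SAP 4.2 (37 + 39 + 10 + 3 + 10 = 99). Dose-group sizes are from Module 1.3.4.1, at 30 November 2019.

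| Group | n | k = 1 | k = 2 | k = 3 |
|---|---|---|---|---|
| All treated | 99 | 1.0 | 2.0 | 3.0 |
| 8 mg/kg every 21 days | 22 | 4.5 | 9.1 | 13.6 |
| 7 mg/kg every 21 days | 9 | 11.1 | 22.2 | 33.3 |
| 9 mg/kg every 21 days | 9 | 11.1 | 22.2 | 33.3 |
| 10 mg/kg every 21 days | 8 | 12.5 | 25.0 | 37.5 |
| 6 mg/kg every 14 days | 6 | 16.7 | 33.3 | 50.0 |

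For serious and Grade 3 or higher TEAEs these are upper limits, because a subject with another such event is already counted.

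The 7 mg/kg group will probably be larger at the final analysis, since the SAP pools Part B with Parts A and A2. If the 3 Part B subjects received the planned 7 mg/kg, n = 9 + 3 = 12 and one death is worth 100 / 12 = 8.3 points.

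**The case against.** The strongest reply is that the two rules may describe much the same events. Module 8.1 concerns progression as the reported event, and the SAP's preferred term is a programmable version of it. Module 8.5 also asks sites, where possible, to name a disease or syndrome and not its separate signs and symptoms, which favours the underlying cancer over a terminal symptom. This may make divergent cases few. It does not fix a term, so it does not make the rules equal.

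A reader might infer that a death reported under its terminal event, such as respiratory failure in a progressing patient, is wrongly kept in the tables. The documents do not support that: such a death is not clearly one reported as due to progressive disease, so Module 8.1 may not reach it. Nor do they show that a site's choice of words decides the outcome. Different verbatim terms can share a preferred term, and the coding conventions are not given.

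A second reply is that no death is hidden. This stands. The listings, including those of fatal TEAEs and of deaths, and the table of deaths by study period carry no stated preferred-term condition. SAP 12.1 plans no inferential safety tests, and the every-21-day recommended dose had been chosen by November 2019. The SAP's narrower exclusion also keeps more deaths in view, which is the cautious direction.

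Third, the mismatch may come from document versions. The SAP is based on Module Amendment 06, under which it describes 7 parts, while the supplied Module has 9. Whether Amendment 06 contained the same sentence cannot be seen. Module 9.2 also refers safety methods to Core Section 11, whose AE section has no progression exclusion. That lets the SAP depart from the Core, but leaves the Module's own sentence unreconciled.

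**Conclusion.** The point holds as an inconsistency between the SAP and the Module. Followed as written, SAP 12.1 can tabulate unrelated deaths reported as due to progressive disease that Module 8.1 excludes. The effect is confined to all-causality fatal, serious and Grade 3 or higher TEAE rates.

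Its size depends on a number that the documents do not give. Per death, the step in the fatal-TEAE rate is about 1 point overall and 11 to 12.5 points in groups of 9 or 8. If every such death was coded to the SAP's term, the effect is zero. A reader might infer a total number of affected subjects, or that progression deaths outnumber treatment-related ones. Neither follows. Module 1.3.4.1 reports 1 treatment-related death among 92 subjects, but nothing gives the number of progression deaths or how they were coded.

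This is a minor correction. It bears on neither dose selection nor the response rate.

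**What to change.** In SAP 12.1, replace the single preferred-term condition with the Module 8.1 rule: exclude fatal SAEs reported as due to progressive disease and judged unrelated to study drug. Identify them from a list of preferred terms or of individual cases fixed before database lock, as the SAP already does with search lists for other event groups. State that the rule applies identically to the overall AE summary table, including the DSMB version, and to all tables by system organ class and preferred term.

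Show the excluded deaths as a separate line in the planned summary of deaths. Fatal, serious and Grade 3 or higher rates can then be read with and without them, which also answers the worry about removing deaths on investigator attribution in an open-label study. If the single term is intended, the SAP should say so and record it as a departure from Module 8.1.

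The cost is a few sentences in the SAP and one short list review before lock.
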